## **ABBREVIATIONS**

AAD – antiarrhythmic drug  
AE – adverse events  
AF – atrial fibrillation  
CA – catheter ablation  
ECG – electrocardiogram  
ICM – implantable cardiac monitor  
IRB – Institutional Review Board  
KCHRRF – Kansas City Heart Rhythm Research Foundation  
MCOT – mobile cardiac outpatient telemetry  
OAC – oral anticoagulation  
SAE – serious adverse events

## **1 STUDY OBJECTIVES**

### **1.1 Primary Objective**

- Evaluate the differences in outcomes between implantable cardiac monitors (ICM) and routine management in patients with atrial fibrillation (AF).
- Freedom from AF and continued anti-arrhythmic drug (AAD) and oral anticoagulation (OAC) use following ICM implantation.

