## **3 STUDY DESIGN**

We propose a multi-center, retrospective study to evaluate the use of ICM versus traditional, non-ICM methods such as ECGs, Holter, and mobile cardiac outpatient telemetry (MCOT) units, referred to as non-ICM from here on out, from 2018 to 2021. The primary outcome will be the evaluation of AF freedom at 12 months with continued AAD and OAC use. Secondary outcomes are described above. This study will be approved by the Institutional Review Board (IRB), and patient consent will not be required due to the nature of the study.

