## **4 SELECTION AND ENROLLMENT OF PARTICIPANTS**

### **4.1 Study Enrollment Procedures**

#### **4.1.1 Screening**

Patients will be identified for screening via diagnosis codes for AF on chart review. This can be easily identified by querying current electronic medical record systems. If needed, patients with ICMs can be identified by lists maintained at each study center of those who undergo ICM insertion.

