#### **4.1.2 Consent and Enrollment**

Patients who meet inclusion and exclusion criteria after screening will be directly enrolled in the study. No randomization will occur, but patients will be separated into an ICM and non-ICM arm. We will enroll approximately 2500 patients [n=1250 (ICM) and n=1250 (non-ICM)] from 2018-2021. No consent will be required due to the nature of the study.

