## **5 STUDY INTERVENTIONS**

### **5.1 Interventions, Administration, and Duration**

No intervention or administration will be performed due to the observational nature of each phase. Charts of patients enrolled in the study will be reviewed for an initial monitoring method, any changes in

management, including AAD, OAC, CA, as per physicians' preference, arrhythmia recurrence, need for redo CA, and AF-related complication, for 12 months after enrollment. Lastly, the primary outcomes of AF freedom and continued AAD and OAC use will be noted at the end of the study duration.

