## 6 STUDY PROCEDURES

### 6.1 Description of Evaluation

*Table 1. Variables for data collection will include but are not limited to the following.*

Variables	Description and Definition
Age	## Years
Gender	0 = Male, 1 = Female
BMI	## kg/m2
Race	0 = Caucasian, 1 = African American, 2 = Hispanic, 3 = Asian, 4 = Other
Hypertension	0 = No, 1 = Yes
Hyperlipidemia	0 = No, 1 = Yes
Diabetes Mellitus	0 = No, 1 = Yes
Coronary Artery Disease	0 = No, 1 = Yes
CVA/TIA	0 = No, 1 = Yes
Peripheral Artery Disease	0 = No, 1 = Yes
Obstructive Sleep Apnea	0 = No, 1 = Yes
Compensated HF (EF > 35%)	0 = No, 1 = Yes
History of Smoking	0 = No, 1 = Yes
Thyroid Dysfunction	0 = None, 1 = Hypothyroidism, 2 = Hyperthyroidism
Chronic Obstructive Pulmonary Disease	0 = No, 1 = Yes
Gastrointestinal Disorders	0 = No, 1 = Yes
CHADS 2 /VASC 2 Score	##
Antiarrhythmic Drug	
History of Cardioversion	0 = No, 1 = Yes
Baseline AAD Use	0 = No, 1 = Yes
Duration of Arrhythmia	## Mos.
Left Atrial Size	## cm.
Left Ventricular Ejection Fraction	## %
Access to EP	0 = No, 1 = Yes
Compliance to OAC	0 = No, 1 = Yes
Attempted AAD	0 = No, 1 = Yes
Need for Catheter Ablation	0 = No, 1 = Yes
Time to Catheter Ablation	## Days
Number of Monitors used Post-CA	##

Type of Monitors Used	0 = MCOT, 1 = 48-Hr Holter
Need for Redo Ablation	0 = No, 1 = Yes
Time to Redo Ablation	## Days
CV-Related Hospital Duration	## Days
Length of Stay	## Days
AF-Related Hospitalization	0 = No, 1 = Yes
HF-Related Hospitalization	0 = No, 1 = Yes
Bleeding Complication	0 = No, 1 = Yes
Stroke and TIA	0 = No, 1 = Yes
Freedom of AF at 12 Mos.	0 = No, 1 = Yes
Continued OAC Use	0 = No, 1 = Yes
Continued AAD Use	0 = No, 1 = Yes

Abbreviations: BMI – body mass index, CVA = cerebrovascular accident, TIA – transient ischemic attack, AAD = antiarrhythmic drug, CV – cardiovascular, CA = catheter ablation, AF – atrial fibrillation, HF – heart failure, OAC – oral anticoagulation, MCOT – mobile cardiac outpatient telemetry

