## 6.3 Follow-up Visits

Follow-up will occur up to 12 months after enrollment into the study. Follow-up visits and management changes will occur at the treating physician's discretion.

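### No time zero applies to both arms: the primary objective counts from ICM implantation, the follow-up sections count from an undated enrollment, and the pre-implant ablation exclusion has no non-ICM counterpart

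*Combined protocol and SAP*

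**What the plan says.** Four parts of the combined protocol and SAP bear on when follow-up starts.

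- **Primary outcome.** The second bullet of 1.1 reads "Freedom from AF and continued anti-arrhythmic drug (AAD) and oral anticoagulation (OAC) use following ICM implantation". Section 3 says "The primary outcome will be the evaluation of AF freedom at 12 months with continued AAD and OAC use" and names no start.
- **Follow-up.** Section 5.1 has charts reviewed "for 12 months after enrollment", and 6.3 says "Follow-up will occur up to 12 months after enrollment into the study". Neither separates the arms.
- **Enrollment.** Section 4.1.2 says "Patients who meet inclusion and exclusion criteria after screening will be directly enrolled in the study". The study is retrospective, and 4.3 removes anyone not followed for more than 12 months. Section 4.1.1 screens by AF diagnosis codes and adds: "If needed, patients with ICMs can be identified by lists maintained at each study center of those who undergo ICM insertion".
- **Eligibility.** Section 4.3 excludes patients whose AF ablation came before ICM implant. It states no equivalent for patients who have no implant.

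Section 9.3 lists times to drug initiation and to catheter ablation (CA) among the primary outcomes, and Table 1 in 6.1 collects "Time to Catheter Ablation" in days. Table 1 lists neither a first-visit date nor an ICM insertion date. Section 9.4 plans t-tests, Mann-Whitney, chi-square and Cox models, with no matching, adjustment or time-varying exposure.

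**The concern.** A 12-month rate or a time to an event needs a starting date that exists for every patient. Implantation exists in one arm only. Enrollment, read as the day a chart passes screening, falls after the required follow-up is complete, so it cannot begin that follow-up. Abstractors at several centres would have to pick a date themselves. For ICM patients the obvious pick is the implant, the only clinical index event that the protocol names. For the others it is some AF-coded visit.

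If the implant tends to fall later in the course of AF than that visit, two things follow. The arms are observed over different stretches of the disease, and early ablations are removed from the ICM arm only. Either could be read as an effect of ICM. Patients who never change arm are affected, so a rule for the crossovers allowed in 9.1 would not cure it.

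**Working it through.** **What the plan supplies.** It gives 1250 per arm (9.2), alpha 0.05 (9.4), the pre-implant CA exclusion (4.3) and 12 months (3, 5.1, 6.3). It gives no timing of implants or ablations, so the timing below is assumed. It also has no figure of its own on this point. The 99% power in 9.2 is a separate matter and cannot be reproduced, because no effect size is stated.

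**Ablation, with identical CA timing in both arms.** Let T be time from first AF visit to CA: 40% ever ablated, lognormal with median 4 months and log-SD 0.6. Let L be time from first visit to implant, uniform over 0 to 6 months. The non-ICM clock starts at the first visit. By simulation:

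- P(T ≤ 12) = 38.7%
- P(T ≤ L) = 13.1% (CA before implant)
- P(T ≤ L + 12) = 39.4%

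| ICM arm handled as | Formula | 12-month CA, ICM | Non-ICM |
|---|---|---|---|
| Clock at implant, prior CA excluded | (39.4 - 13.1)/(100 - 13.1) | 30.3% | 38.7% |
| Same clock as non-ICM, prior CA excluded | (38.7 - 13.1)/(100 - 13.1) | 29.5% | 38.7% |
| Clock at implant, prior CA kept as an event | P(T ≤ L + 12) | 39.4% | 38.7% |

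The gap of 38.7 - 30.3 = 8.4 points therefore comes from the one-sided exclusion. The clock shift moves the rate by under 1 point, in the other direction.

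**Time to CA among those ablated within 12 months.** The mean is 4.4 months non-ICM v 3.2 months ICM. With a common clock and the same exclusion the ICM mean would be about 5.3 months, so the shorter ICM time is produced by the later origin.

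**Chance of declaring the 8.4 points significant.** The pooled proportion is (0.387 + 0.303)/2 = 0.345. The null SE is √(2 × 0.345 × 0.655/1250) = 0.0190, and the SE under the difference is 0.0189. Then (0.084 - 1.96 × 0.0190)/0.0189 ≈ 2.47, which is power of about 99%.

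**Sensitivity.** With median time to CA from 2 to 9 months and implants spread over 3, 6 or 12 months, the ICM minus non-ICM difference runs from about +2.5 points (median 9, implants over 6 months) to about -28 (median 2, implants over 12 months).

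**AF freedom, with no ICM effect.** Assume Weibull time to recurrence with 60% free at 12 months: S(t) = exp[-0.511 (t/12)^k]. ICM patients start s months later, still event-free, so their 12-month freedom is S(12 + s)/S(s).

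| Shape k | s = 3 months | s = 6 months | Rejection probability, 1250 per arm |
|---|---|---|---|
| 0.8 (falling hazard) | 0.543/0.845 = 64.3% | 0.493/0.746 = 66.2% | 59%; 89% |
| 1.0 (constant) | 60.0% | 60.0% | 5%; 5% |
| 1.2 (rising) | 0.513/0.908 = 56.5% | 0.436/0.801 = 54.4% | 43%; 81% |

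**After the fix.** When non-ICM patients are indexed at the same elapsed times and are CA-free at that point, the ablation model gives 30.2% v 30.2%.

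**The case against.** The best defence is that the plan does not assign separate clocks. Sections 5.1 and 6.3 apply enrollment to everyone, and 1.1 is an objective, not a follow-up rule. That stands. A reader might infer that the ICM arm is measured from implant and the non-ICM arm from enrollment, but no section says so. What the text shows is a conflict between 1.1 and 5.1/6.3, plus an undated enrollment. If the 2018 to 2021 enrollment period in 4.1.2 refers to a clinical date, the plan does not say which one.

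The lag is also an inference. Diagnosis codes screen both arms, implant lists are used only if needed, and 4.2 does not require a new presentation. Non-ICM patients could be long-standing cases, so even the direction is unknown. Table 1 is not exhaustive and does collect arrhythmia duration, though with no measurement date and no stated use in the analysis.

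A reader might further infer that 12-month results must differ, or that the 8-point ablation gap measures the clock difference. Neither is supported. A later start in event-free patients gives no bias under a constant hazard and can go either way otherwise. The ablation gap comes from the exclusion.

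Finally, a matched index date is not the only remedy. A common first-visit date with ICM as a time-varying exposure is also valid. That affects the choice of fix, not the need for one.

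**Conclusion.** The point holds as an undefined and inconsistent time zero, made worse by an eligibility rule that can be applied to only one arm. Both are plain in the text, and nothing in 9.4 corrects them. Biased 12-month and time-to-event comparisons are a risk, not a certainty. They require ICM patients to be indexed later than non-ICM patients, together with either the one-sided exclusion or a hazard that changes over the course of AF.

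Under the assumed timing the false ablation difference is about 8 points, and mean time to ablation differs by 4.4 - 3.2 = 1.2 months. Those figures show what is possible and do not predict this study's result. It should be fixed before chart abstraction, because the primary comparison cannot be interpreted without a common origin.

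**What to change.** Define one time zero in 1.1 and use it in 5.1 and 6.3 wherever enrollment now starts the 12 months.

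1. For ICM patients, time zero is the implant date.
2. Each non-ICM patient gets an index date at the same elapsed time since first AF-management visit as an ICM patient from the same centre. Choose the match from patients who are free of ICM and CA on that date.
3. Apply every criterion in 4.2 and 4.3 at time zero in both arms, including no prior CA and the follow-up requirement.
4. Count every 12-month and time-to-event outcome from time zero in both arms.
5. Add the dates of first AF-management visit and ICM insertion to Table 1.
6. State alongside this how a matched non-ICM patient who later receives an ICM is analysed, since 9.1 allows it.

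The cost is revised wording, two dates per chart, the matching work, and the loss of a few ICM patients with no comparable non-ICM patient. Done after abstraction, it would mean reopening about 2500 charts.

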### **1.2 Secondary Objectives**

- To evaluate differences in catheter ablation (CA) and AAD for rhythm control and AF-related complications in those with and without ICM.

## **2 BACKGROUND AND RATIONALE**

### **2.1 Background on Condition, Disease, or Other Primary Study Focus**

AF is the most frequent cardiac arrhythmia, with a global prevalence that is only expected to increase. A significant number of patients – up to 38% – may be asymptomatic, making management more difficult. [1] Regardless of symptoms, AF is associated with significant morbidities, including but not limited to heart failure, stroke, dementia, and death.

The management of AF is complex, with clinical decisions related to rate and rhythm control strategies with AADs and CA and stroke prevention. Like other chronic diseases, frequent routine assessments help select, assess, and change management strategies. Implantable cardiac monitors (ICMs) are another option that store electrocardiogram (ECG) tracings for years at a time, enabling continuous monitoring, assessment of AF burden, and therapy efficacy. Previous studies have demonstrated a threefold increase in AF detection, including asymptomatic AF in cryptogenic stroke, syncope, and after CA. using ICMs.[2-4] Their use in AF management has gained popularity for this reason.

### **2.2 Study Rationale**

Even with its increasing popularity and use, the impact of ICMs on AF management is still being determined and can even be conflicting. Furthermore, the use of ICM is dependent on physician preference. We hypothesize that dynamic monitoring with ICMs is superior to conventional methods and should be used for all patients with AF. Thus, we aim to measure the outcomes of using ICM versus more traditional approaches in patients with AF.

## **3 STUDY DESIGN**

We propose a multi-center, retrospective study to evaluate the use of ICM versus traditional, non-ICM methods such as ECGs, Holter, and mobile cardiac outpatient telemetry (MCOT) units, referred to as non-ICM from here on out, from 2018 to 2021. The primary outcome will be the evaluation of AF freedom at 12 months with continued AAD and OAC use. Secondary outcomes are described above. This study will be approved by the Institutional Review Board (IRB), and patient consent will not be required due to the nature of the study.

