### **4.3 Exclusion Criteria**

- Patients < 18 years of age
- Presence of a permanent pacemaker, implantable cardiac defibrillator, or cardiac resynchronization therapy
- Unable to tolerate ICM or traditional monitoring with ECG, Holter, or MCOT monitoring
- Unable to tolerate AAD, OAC, and CA as part of AF standard of care
- ICM inserted for cryptogenic stroke or syncope
- Was not followed > 12 months
- CA performed for AF before ICM implant

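### AF freedom and arrhythmia recurrence are compared between arms that differ by rhythm monitor, with no common detection rule, so the comparison carries a detection component against ICM

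*Combined protocol and SAP*

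**What the plan says.** Section 3 compares ICM with ECG, Holter and MCOT monitoring in a retrospective study and sets the primary outcome: "The primary outcome will be the evaluation of AF freedom at 12 months with continued AAD and OAC use". Section 9.3 lists arrhythmia recurrence among the primary outcomes; AF freedom does not appear in that list.

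Both outcomes come from chart review. Section 5.1 covers "arrhythmia recurrence, need for redo CA, and AF-related complication, for 12 months after enrollment" and then says that "the primary outcomes of AF freedom and continued AAD and OAC use will be noted at the end of the study duration". Table 1 in section 6.1 carries "Freedom of AF at 12 Mos" as a yes/no item. Its monitor-type field has two codes, MCOT and 48-hour Holter, and no listed field holds the source of an AF detection. The table says its list is not exhaustive. Section 6.3 leaves visits to the treating physician.

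On the monitors themselves, section 2.1 describes ICMs as "enabling continuous monitoring, assessment of AF burden, and therapy efficacy" and adds: "Previous studies have demonstrated a threefold increase in AF detection, including asymptomatic AF in cryptogenic stroke, syncope, and after CA".

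Section 9.4 plans t-tests, Mann-Whitney and chi-square tests, Cox models with no named covariates, and Kaplan-Meier curves. Section 9.1 lets non-ICM patients cross into the ICM group.

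**The concern.** The exposure is also the instrument that measures the outcome. If a patient's AF is found by the ICM but would have been missed by intermittent recording, that patient counts as a failure in one arm and as AF-free in the other, with the same heart rhythm. No section says which source counts as AF or asks for the same source in both arms.

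Section 2.2 hypothesises that ICM is superior. On these two outcomes the detection component runs the other way: it can produce a false deficit for ICM or hide a true benefit. A larger sample does not help, because it makes a false difference more likely to reach significance. Covariates in a Cox model would not cure it either, because the error lies in how the outcome is measured.

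The time frame is also open. Section 5.1 reviews recurrence over 12 months but notes AF freedom at the end, so AF freedom could be cumulative or a status at month 12. The documents also do not say whether recurrence applies to all patients or only after ablation. The size of the problem differs between these readings.

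**Working it through.** **The plan's own figure.** Section 9.2 gives 99% power for 2500 patients. It cannot be reproduced, because no AF rate or effect size is stated. Solving backwards, 1250 per arm gives 99% power (two-sided 0.05) for a difference of 5.7 points at a reference rate of 10%, 7.3 at 20%, 8.1 at 30% and 8.5 at 40% to 50%.

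**Inputs.** From the documents: 1250 per arm (section 9.2) and p<0.05 (section 9.4; two-sided assumed for proportions). Assumed, because the documents give no values: equal true AF rate r in both arms, full ICM detection, detection ratio k (ICM to non-ICM), and the AF component alone without AAD and OAC use.

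The threefold figure in section 2.1 is not used for k. It is quoted for stroke, syncope and post-ablation settings together, and section 4.3 excludes "ICM inserted for cryptogenic stroke or syncope".

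**Formulas.** Observed AF is r with ICM and r/k without. The false gap is d = r(1 − 1/k). The chance of p<0.05 is about Φ[(d − 1.96·SE0)/SE1], plus a negligible or small opposite tail, where SE0 uses the pooled rate and SE1 the separate rates.

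**One case in full.** r = 0.30, k = 1.2: observed 0.30 v 0.25, d = 0.05, pooled rate 0.275. SE0 = √(0.275 × 0.725 × 2/1250) = 0.01786. SE1 = √[(0.30 × 0.70 + 0.25 × 0.75)/1250] = 0.01783. (0.05 − 1.96 × 0.01786)/0.01783 = 0.84, and Φ(0.84) = 0.80.

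**Range, 1250 per arm, no crossover.**

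| k | Cumulative, r = 20% to 45%: gap (points) | p<0.05 | Month-12 status, r = 5% to 20%: gap (points) | p<0.05 |
|---|---|---|---|---|
| 1.05 | 1.0 to 2.1 | 9% to 19% | 0.2 to 1.0 | 6% to 9% |
| 1.1 | 1.8 to 4.1 | 21% to 54% | 0.5 to 1.8 | 8% to 21% |
| 1.2 | 3.3 to 7.5 | 58% to 97% | 0.8 to 3.3 | 17% to 58% |
| 1.5 | 6.7 to 15 | 99% or more | 1.7 to 6.7 | 55% to 99% |

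**Smaller denominators.** If recurrence applies only to ablated patients, whose number is not given, an assumed 500 per arm (cumulative) gives 28% to 67% at k = 1.2 and 81% to about 100% at k = 1.5. An assumed 250 per arm gives 16% to 40% and 52% to 94%.

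**Crossover.** With an assumed 25% crossing over and analysed as initially assigned, the non-ICM rate is 0.25r + 0.75r/k. On the cumulative reading at k = 1.2 the chance is 36% to 81%, against 58% to 97% without crossover: diluted, not removed.

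**Masking.** A true 30% (non-ICM) v 25% (ICM) looks equal at k = 1.2, since 30%/1.2 = 25%.

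**The case against.** Several points on the other side are fair.

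- **Monitoring is partly recorded.** Section 5.1 abstracts the initial monitoring method, and Table 1 counts monitors used after ablation. The monitor-type field may simply classify external monitors, so the lack of an ICM code is weak evidence. This stands, but recording some monitoring is not a rule for which detections count.
- **Adjustment is unspecified, not ruled out.** True of the Cox models in section 9.4, but covariates would not remove unequal detection.
- **Section 1.1 can be read as descriptive.** Its second objective speaks of AF freedom following ICM implantation, which could mean the ICM arm only. Section 3, which sets the outcome within an ICM versus non-ICM design, favours a between-arm reading, and recurrence is a primary outcome in section 9.3 either way.
- **More detection is what an ICM is for.** That supports describing ICM-detected AF. It does not make more detected AF a worse outcome.
- **The detection ratios are assumptions.** They are, and at 1.05 the month-12 status result is close to nominal.
- **A common-source endpoint can reverse the bias.** If the ICM replaces ECG, Holter or MCOT recordings, dropping ICM-only detections under-counts AF in the ICM arm. An assumed 15% v 12% at 1250 per arm gives p<0.05 in about 59%, in favour of ICM. This stands, so a common-source analysis should not be the sole main comparison.

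A reader might infer more than the documents support. One inference is that no result on these outcomes could be interpreted. That is too broad, because a result favouring ICM would arise against this component. Another is that section 2.1's threefold figure sizes the bias; section 4.3 excludes two of its three settings. A third is that the net bias must run against ICM; physician choice of ICM (section 4.2) and crossover may act differently. A fourth is that AAD, OAC or redo-ablation findings are equally artefactual; these may be real consequences of ICM information.

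**Conclusion.** The concern holds for AF freedom at 12 months and arrhythmia recurrence. As written, the plan builds a detection component against ICM into both comparisons. An ICM deficit or a null on them cannot be taken as harm or absence of benefit from ICM-guided management. A result favouring ICM would have overcome this component but would remain exposed to confounding by indication.

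The existence and direction of the component follow from the documents; its size does not. The tabulated probabilities run from near nominal to near certainty, depending on the detection ratio, the true AF rate and which reading of AF freedom applies. They rest on equal true AF, full ICM detection and no crossover unless stated. The net direction of all biases together is not established.

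**What to change.** 1. State whether AF freedom is cumulative or status at month 12, and whether recurrence applies to all patients or only after ablation.
2. Abstract the source (ECG, Holter, MCOT, ICM, hospitalisation) and date of each AF detection, and the number and type of non-ICM recordings per patient in both arms.
3. Report each comparison two ways, side by side: all sources, labelled as biased against ICM; and only sources available in both arms (ECG, Holter, MCOT), excluding ICM-only detections. Apply the same rule to patients who cross over.
4. State that the common-source version can be biased either way, since alerts can prompt extra ECGs and the ICM can replace external recordings. Show recording counts by arm.
5. Draw no conclusion of superiority, harm or no difference on these two outcomes unless both versions agree. Read them beside thromboembolic events and cardiovascular mortality. Mortality helps only if early deaths are kept, and section 4.3 excludes a patient who "Was not followed > 12 months".

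**Cost.** Protocol and SAP wording, plus extra abstraction from about 2500 charts already under review; no new patients or procedures. Some charts may not record the source. The common-source analysis loses power: for a true 45% v 40% at 1250 per arm, 72% falls to 46% if common sources catch 1/1.5 of events (30% v 26.7%), and to 22% if they catch 1/3 (15% v 13.3%). Alert-prompted ECGs leave residual bias: an assumed 15% v 16.5% gives p<0.05 in 18%. Confounding by indication is not addressed.
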